6.4 Secondary Endpoint Analysis

S1: Compare the change in mean HF symptom severity scores at baseline and 12 week as measured by Kansas City Cardiomyopathy Questionnaire (KCCQ) among patients randomized to remote CR versus usual management.

Analysis Strategy for S1: The outcome variable for this objective is the mean change in HF symptom severity scores from 1 week before randomization (baseline) to 12 weeks, calculated as the HF symptom severity scores in week 12 minus the mean of baseline period. The hypothesis test will evaluate whether the mean change in the remote CR treatment group is different from the mean change in the usual management group. The test will be a two-sample t-test allowing for unequal variances.

Reporting for S1: Descriptive summaries of the mean physical activity at baseline and 12 weeks, as well as the 12-week change mean will be presented by treatment group. The summary statistics of the score at baseline, at 12-weeks and change from baseline will be reported for each treatment group. The mean difference (95% CI) between the CR and usual care treatment groups for change from baseline will be presented, along with the t-test p-value. If differences are noted with regard to baseline covariates adjusted analyses will be performed for the Secondary endpoint.

S2: (Safety) Report Adverse Events of heart failure hospitalization, fracture, myocardial infarction, serious adverse arrhythmia, and ICD therapy among randomized patients .

Reporting for S2: A listing of Adverse Events will be produced for the study population.

S3: Investigate the correlation between change in daily PA as measured by the Abbott ICD or CRT-D device between baseline and week 12 after randomization and change in HF symptoms severity scores as measured by KCCQ during same time period.

Analysis Strategy for S3: The variables used for this objective are the change in median PA from baseline to week 12, and the change in HF symptom severity score from baseline to week 12. The hypothesis test will evaluate whether there is a correlation between these two variables, pooling subjects across treatment groups..

Reporting for S3: We will be reporting the strength of the correlation and related p value and 95% CI.

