### 3.2 SECONDARY OBJECTIVES

- Baseline and follow up KCCQ quality of life survey scores will be compared between treatment groups.
- To assess safety of the intervention, we will report AEs between treatment groups.

No adjusted analyses will be performed for comparisons of secondary outcomes.

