## 9 STUDY OUTCOMES

### 9.1 AIMS

**Aim 1:** Compare the mean Abbott ICD and CRT-D device measured daily PA obtained over the 1 week before randomization (baseline) and 12 weeks after randomization among patients randomized to remote CR versus usual management. This objective was chosen to determine if it is possible to objectively measure a clinically meaningful change in PA using an ICD or CRT-D device. Further, the primary objective assesses whether a remotely administered exercise training program can increase the observed PA over a relatively short time interval.

**Aim 2:** Compare baseline and 12 week Kansas City Cardiomyopathy Questionnaire (KCCQ) HF symptom severity scores among patients randomized to remote CR versus usual management. This objective was chosen to determine if the remotely administered exercise training is associated with subjective improvement in HF symptoms. This endpoint has been used previously in studies of exercise training in patients with HF, so we should be able to compare the direction and magnitude in change in our study to results obtained in prior studies.

**Aim 3:** (Safety) Report Adverse Events of heart failure hospitalization, fracture, myocardial infarction, serious adverse arrhythmia, and ICD therapy among patients randomized to remote CR versus usual management. This objective is important since little data are available regarding the safety of starting an exercise training program without a prior CPET study. We will determine if patients randomized to exercise training experience excess risk.

**Aim 4:** Measure the correlation between change in daily PA measured by the Abbott ICD or CRT-D device between baseline and end of follow up and change in KCCQ HF symptoms severity score measured between baseline and end of follow up. This objective will allow us to determine what change in device measured PA is associated with an improvement in QOL.

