#### 11.1.2 OVERALL STATISTICAL APPROACH

All tests will be tested in no particular sequence. There will be no interim analysis. As this is a hypothesis generating study, we will not employ a mechanism to address alpha spending (multiplicity) within the secondary endpoint family.

For P1 and S1-S2, we will be reporting 95% confidence intervals, mean at baseline, mean at terminal timepoint, Multilevel Model estimates over the timepoints of interest, and related p values.

For the S3, we will be reporting the strength of the correlation and related p values.

Additionally, alpha levels will be set at 0.05, and all tests will be two sided unless otherwise stated. All these statistics will be obtained via SAS 9.4 or higher. Please see Section 11.2 for how continuous and categorical variables will be reported. Values obtained from scheduled measurement time points will be included in data summaries tables and listings. We will utilize the Shapiro-Wilk or goodness of fit tests to assess normality.

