4.1.1 Analysis Population

Effectiveness will be assessed in the Intent-To-Treat (ITT) population and in the As-treated (AT) populations. Both analysis populations will be examined for all objectives, however, the success of the trial will be based on the analysis of the ITT population.

- Intent-to-Treat (ITT) Population: All participants who were randomized. Subjects will be analyzed according to the treatment group to which they were randomized, regardless of whether they received that intervention. This population will include participants who may have received the wrong intervention and have protocol violations.
- Safety Analysis (SA) Population: All participants who had at least one session on the study app.
- As-Treated (AT) Population: The treatment assignment of this population will be based on the actual treatment patients received, not the treatment the patients were randomized to receive.

Deviations related to treatment compliance with randomized intervention: Participants not meeting the adherence requirement of completing at least 2/3 of expected app check in sessions will be considered a protocol deviation and excluded from the AT analysis population.

Any additional exclusion of any subject from a data presentation, other than those described above and in the section on handling of missing data, will be considered on a case-by-case basis, and will be described in the final study report.

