7 TABLES, FIGURES, AND LISTINGS

Table	Title	Population
1. Disposition		
Table 1	Subject Enrollment and Status Summary	All enrolled
2. Demographics and Past Medical History		
Table 2.1	Demographics and Baseline Characteristics	ITT
Table 2.2	Demographics and Baseline Characteristics	AT
Table 2.3	Medical History at Baseline	ITT
Table 2.4	Medical History at Baseline	AT
3. Primary Endpoint Analysis		
Table 3.1.1	Primary Endpoint P1: Trajectory of the median Abbott ICD and CRT-D device measured daily PA obtained over baseline and treatment period	ITT
Table 3.1.2	Primary Endpoint P1: Descriptive statistics of the median Abbott ICD and CRT-D device measured daily PA obtained over baseline and treatment period	ITT
Table 3.2.1	Primary Endpoint P1: Trajectory of the median Abbott ICD and CRT-D device measured daily PA obtained over baseline and treatment period	AT
Table 3.2.2	Primary Endpoint P1: Descriptive statistics of the median Abbott ICD and CRT-D device measured daily PA obtained over baseline and treatment period	AT
Table 3.3	P1: Sensitivity Analysis for Imputed Data	ITT
Table 3.4*	P1: Sensitivity Analysis for Transformed Data	ITT
4. Secondary Endpoint Analysis		
Table 4.1.1	Secondary Endpoint S1: Change from baseline KCCQ HF symptom severity score to the last week of study	ITT
Table 4.1.2	Secondary Endpoint S1: Change from baseline KCCQ HF symptom severity score to the last week of study	AT
List 4.2	Secondary Endpoint S2: Adverse Events: heart failure hospitalization, fracture, myocardial infarction, serious adverse arrhythmia, and ICD therapy	ITT and AT
Table 4.3.1	Secondary Endpoint S3: Association between daily PA measured by the Abbott ICD or CRT-D device and in KCCQ HF symptoms severity score measured between baseline and end of follow up	ITT
Table 4.3.2	Secondary Endpoint S3: Association between daily PA measured by the Abbott ICD or CRT-D device and in KCCQ HF symptoms severity score measured between baseline and end of follow up	AT

*These tables will be intentionally blank if sensitivity analysis unnecessary.

Figure	Title	Population
Figure 3.1.1	Predicted Trajectories of the Mean Abbott ICD and CRT-D Device Measured Daily PA by Random Group	ITT
Figure 3.1.2	Trend of the Median Abbott ICD and CRT-D Device Measured Daily PA by Random Group	ITT
Figure 3.2.1	Predicted Trajectories of the Mean Abbott ICD and CRT-D Device Measured Daily PA by Random Group	AT

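### Aim 3 promises a between-arm safety assessment, but the S2 analysis specifies only a listing, and no output at this sample size can determine excess risk

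*SAP*

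**What the plan says.** **What is promised.** Protocol 9.1 sets Aim 3 as a comparison. It reports events up to and including "ICD therapy among patients randomized to remote CR versus usual management", and adds: "We will determine if patients randomized to exercise training experience excess risk". The reason given is that few data exist on starting exercise without a prior cardiopulmonary exercise test. The text after the aims says that all four will inform a pivotal trial. Protocol 3.2 states: "To assess safety of the intervention, we will report AEs between treatment groups". Protocol 11.1.2 goes further: "For P1 and S1-S2, we will be reporting 95% confidence intervals, mean at baseline, mean at terminal timepoint", followed by multilevel-model estimates and p values. S2 is the adverse-event endpoint.

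**What is planned.** Protocol 11.8.2 and SAP 6.4 give the same single line of reporting for S2: "A listing of Adverse Events will be produced for the study population". In SAP Section 7 the only safety entry is List 4.2, "Secondary Endpoint S2: Adverse Events: heart failure hospitalization, fracture, myocardial infarction, serious adverse arrhythmia, and ICD therapy", to be run on the ITT and As-Treated (AT) sets. There is no safety table.

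**Populations.** SAP 4.1.1 defines a set for safety, "Safety Analysis (SA) Population: All participants who had at least one session on the study app", but no entry in Section 7 uses it. The AT set, which Section 7 does use, leaves out patients who complete fewer than two thirds of their app check-ins.

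**The concern.** A stated aim has no analysis that delivers it. For P1 and S1 the SAP says that results are summarised by treatment group; for S2 it does not. SAP 3.2.2 narrows the objective to reporting events of the remote programme, with no comparator. Yet SAP 5.1 says that nothing departing from the protocol affects the analysis.

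Protocol 11.1.2 points the other way, but with the wrong tools. Baseline means, terminal means and trajectories do not suit an endpoint that counts patients with an event. An analyst cannot follow 11.1.2 and 11.8.2 together.

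Some choices are therefore left open: the denominator, whether the events are combined, whether patients or events are counted, and the interval method. The trial is unblinded (Protocol 4.3) and has no DSMB (Protocol 10.3 and 12.5), so these choices would be made by people who know the allocation and the events. A short or empty listing without an interval also gives the pivotal-trial team no measure of how much risk remains compatible with the data.

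**Working it through.** **Step 1. The plan's own figure.** There is none to reproduce. Protocol 11.4 and SAP 4.2 give power for Aims 1 and 2 only. Neither document states an event rate, power or precision for safety.

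**Step 2. The texts side by side.**

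| Place | What S2 or Aim 3 gets |
|---|---|
| Protocol 3.2 | Events by arm |
| Protocol 9.1 | A conclusion on excess risk, remote CR against usual care |
| Protocol 11.1.2 | 95% CIs, means, multilevel estimates, p values |
| Protocol 11.8.2 | A listing; the events are described as a combination |
| SAP 3.2.2 | Report events; no comparator |
| SAP 6.4 | A listing; no longer described as a combination |
| SAP 7, List 4.2 | A listing, ITT and AT |

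The first three promise a comparison or an interval. The last four do not provide one.

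**Step 3. What a by-arm table could show.**

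Inputs: SAP 4.1 gives 13 patients and the protocol gives 50; both use 1:1 allocation. I take 25 per arm for 50. For 13 I assume 7 on remote CR and 6 on usual care.

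*No events in an arm.* The upper end of the exact two-sided 95% interval for 0/n is 1 − 0.025^(1/n).

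- n = 7: 1 − 0.025^(1/7) = 41.0%
- n = 6 (if the split goes the other way): 1 − 0.025^(1/6) = 45.9%
- n = 25: 1 − 0.025^(1/25) = 13.7%

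*Illustration at 13 patients: 1/7 against 0/6.* The difference is 14.3 points. The Wilson limits are 0.026 to 0.513 for 1/7, and 0 to 0.390 for 0/6. Newcombe's interval is:

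- lower: 0.143 − √[(0.143 − 0.026)² + (0.390 − 0)²] = −0.26
- upper: 0.143 + √[(0.513 − 0.143)² + (0 − 0)²] = 0.51

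*Illustration at 50 patients: 5/25 against 2/25.* The difference is 12 points. The Wilson limits are 0.089 to 0.391 and 0.022 to 0.250. Newcombe's interval is:

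- lower: 0.12 − √[(0.200 − 0.089)² + (0.250 − 0.080)²] = −0.08
- upper: 0.12 + √[(0.391 − 0.200)² + (0.080 − 0.022)²] = 0.32

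*How often the listing would be empty.* If every patient had the same risk p, the chance of no event in 13 patients is (1 − p)^13. This is 51% at p = 5%, 25% at 10% and 5.5% at 20%. These risks are assumptions, since the documents give none.

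**Step 4. Reading the result.** Both illustrative intervals for the difference run from a benefit to a large harm. A by-arm table would describe the uncertainty properly, but it would not determine whether there is excess risk.

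**The case against.** The strongest reply is that S2 is descriptive on purpose. Protocol 11.1.1 states hypotheses for P1, S1 and S3 and none for S2, and both documents call the study hypothesis generating. With 13 patients, anyone holding the patient-level listing and the assignments could tally events by arm. The columns of List 4.2 are not given, so it may well show arm. SAP 6.1.1 also says that categorical variables are presented as counts and percentages, though it does not say by arm.

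Much of this stands, and it rules out several stronger readings that a reader might infer:

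- *That the listing is why the safety question cannot be answered.* It is not. The sample size is the binding limit, and a by-arm table would meet the same limit.
- *That the plan has no intention to compare arms.* Protocol 3.2, 9.1 and 11.1.2 all express one. The fault is that the sections specifying the output do not carry it through.
- *That running the listing on AT loses events.* It does not lose them overall. List 4.2 is also run on ITT, which keeps every randomised patient. AT is a poor safety set, because a patient who stops using the app after an event could drop out of it.
- *That low power for a between-arm test is the measure of the problem.* No safety test is specified for S2 beyond the blanket p-value sentence in Protocol 11.1.2, and any power figure would rest on assumed event rates. Interval width is the relevant measure.

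What the reply does not meet is the wording of Aim 3, which promises a determination and not a description. A tally made afterwards is also not a prespecified summary.

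**Conclusion.** The point holds as an unreconciled mismatch. Aim 3 and Protocol 3.2 and 11.1.2 promise a between-arm safety assessment with intervals, while Protocol 11.8.2, SAP 6.4 and SAP Section 7 specify a listing and no by-arm summary. The Safety Analysis population is defined and tied to no output. Separately, Aim 3 claims more than any output could support: zero events would leave a true risk of up to 41% in an arm of 7, or 13.7% in an arm of 25.

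The zero-event limits need only the arm sizes. The 7 and 6 split is assumed, and both totals are shown because the documents disagree on the number of patients. The 1/7 against 0/6 and 5/25 against 2/25 results are illustrations, not predictions.

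The change should be made. It does not touch the primary analysis.

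**What to change.** 1. **SAP 6.4 and Section 7.** Add one table by arm, in all randomised patients, analysed as randomised. For the composite and for each component give the number of patients with at least one event, the number of events, and an exact (Clopper-Pearson) 95% interval per arm. Add the risk difference with a Newcombe or exact 95% interval, naming the method in advance. Plan no hypothesis test. Keep the listing as support, with assigned arm as a column.
2. **Safety set.** Drop AT from List 4.2. Either remove the Safety Analysis definition or state that no output uses it.
3. **Protocol 11.1.2.** Take S2 out of the sentence on means, multilevel estimates and p values.
4. **Protocol 9.1, Aim 3.** Replace the promise to determine excess risk with a promise to estimate event rates by arm with 95% intervals. Bring SAP 3.2.2 into line. Protocol 12.5 calls safety Aim 4 and should be corrected at the same time.

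The cost is one table, no new data, and a minor protocol wording amendment, which Protocol 13 requires the IRB to approve in writing before it is implemented. The safety claim becomes more modest.

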### 11.8.2 SECONDARY ENDPOINT ANALYSIS

General statistical approach to secondary endpoints: These endpoints will be analyzed in both the ITT and PP populations. We will not be using methods to account for multiplicity (alpha sharing plan) as this is a hypothesis generating rather than a confirmatory study. Missing data will be handled as described in Section 11.12.

Analysis Strategy for S1: Will be similar to what is described for P1 with different endpoints.

S1: Compare the change in mean HF symptom severity scores at baseline and 12 week as measured by Kansas City Cardiomyopathy Questionnaire (KCCQ) among patients randomized to remote CR versus usual management.

Reporting for S1: Will be similar to what is described for P1 with different endpoints. If differences are noted with regard to baseline covariates adjusted analyses will be performed for the secondary endpoints.

**S2: (Safety) Report Adverse Events of the combination of heart failure hospitalization, fracture, myocardial infarction, serious adverse arrhythmia, and ICD therapy.**

Reporting for S2: A listing of Adverse Events will be produced for the study population.

**Analysis Strategy for S3:** This analysis strategy will be implemented for the S4 analyses. The outcome variable for this objective is the HF symptoms severity score as measured at baseline through end of follow up. This endpoint represents repeated measures. The hypothesis test will evaluate whether there is a correlation between these treatment groups. If data are normally distributed, the test will be a Pearson correlation test. Otherwise, we will use a Spearman correlation test.

**S3: Investigate the correlation between change in daily PA as measured by the Abbott ICD or CRT-D device between baseline and end of follow up and change in HF symptoms severity scores as measured by KCCQ during same time period.**

Reporting for S3: We will be reporting the strength of the correlation and related p values.

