4.2 Sample Size and Power

Sample size was determined based on the following power calculations:

For aim 1, a sample size of 28 subjects with 1:1 randomization each measured at 4 time points provides 81.1% power to detect a 15 minute per day difference in PA between groups at week 12 with a standard deviation of 19 minutes per day within each group and a within subject correlation of 0.7. A test based on a mixed-model analysis is anticipated at a significance level of 0.05.

For aim 2, a sample size of 50 subjects with 1:1 randomization provides 80.2% power to detect an 8% difference in KCCQ score between groups with a standard deviation of 10 in KCCQ score within each group and an alpha of 0.05.

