6 STATISTICAL ANALYSIS

6.1 General Considerations

6.1.1 General Analysis Conventions

Categorical variables will be presented as counts and percentages of non-missing values. Continuous variables will be presented as means, standard deviations, medians, as well as minimums and maximums, and the number of non-missing values. Missing data will be handled as outlined in section 6.8. Unscheduled assessments will not be included in analyses, but may be included in listings. Appropriate rounding will be performed for the summary statistics. The number of significant digits for the mean and standard deviation will be one and two more than the number for the reported values, respectively. Minimum and maximum values will be presented with the same precision as the original data. Percentages will be presented with one decimal. All statistical tests will be two sided unless stated otherwise. Histograms will be used to assess the normality of the data. Unless otherwise specified below, baseline values will be the last collected value prior to device use.

Statistical tests used will be two-sided, with $\alpha=0.05$ as the level of significance. An absolute magnitude of the correlation coefficient that is 0.1-0.29 indicating weak correlation, 0.3-0.49 as moderate correlation and 0.5-1.0 as strong correlation.

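### Aim 4 sets out to find what PA change goes with a QOL improvement, but S3 reports only a pooled correlation, which has no units and combines the arm difference with the association within arms

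*SAP*

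**What the plan says.** Aim 4 in Protocol 9.1 is to measure the correlation between the change in device PA and the change in the KCCQ symptom score. The section then gives the reason: "This objective will allow us to determine what change in device measured PA is associated with an improvement in QOL". The text following the aims says that the results of Aims 1 to 4 will be used to design a larger pivotal trial.

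SAP 6.4 sets out the analysis under S3. On the PA side, "The variables used for this objective are the change in median PA from baseline to week 12"; on the other side is the KCCQ change over the same period. Then: "The hypothesis test will evaluate whether there is a correlation between these two variables, pooling subjects across treatment groups". The output is fixed as follows: "We will be reporting the strength of the correlation and related p value and 95% CI". SAP 6.1.1 attaches words to the size of the coefficient: "0.1-0.29 indicating weak correlation, 0.3-0.49 as moderate correlation and 0.5-1.0 as strong correlation".

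Protocol 11.8.2 names the coefficient: "If data are normally distributed, the test will be a Pearson correlation test. Otherwise, we will use a Spearman correlation test". The SAP names neither for S3. SAP 6.6 rules out imputation for S3, so it uses complete cases. Tables 4.3.1 and 4.3.2 in SAP section 7 are association tables for the ITT and AT populations. Neither document plans, for S3, a regression slope, a defined size of QOL improvement, a by-arm or partial correlation, or a treatment term.

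**The concern.** There are two parts.

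First, the purpose needs an answer in units: how many minutes of daily PA go with how many KCCQ points. A correlation, its p value and its CI all describe the same unitless quantity. The same r is compatible with very different minutes-per-point figures, depending on the spread of the two changes.

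Second, S3 has one pair of changes per patient and pools both arms without a treatment term. The coefficient therefore has two sources: the association among patients in the same arm, and the shift between arms. The CR arm also gets medication reminders, healthy-eating resources and behavioural advice (Protocol 8.4.2). The trial is unblinded (Protocol 4.3) and the KCCQ is self-administered (Protocol 9.2.2). Treatment could therefore move KCCQ by routes other than PA, and part of the pooled r could reflect that.

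At stake is whether the pivotal-trial team gets a usable conversion from PA to KCCQ. The primary endpoint is not affected.

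**Working it through.** **Inputs.** From SAP 4.2, the Aim 1 calculation is built to "detect a 15 minute per day difference in PA between groups at week 12". Its spread inputs are an SD of 19 min/day in each arm and a correlation of 0.7 between repeated values on the same patient. The planned KCCQ effect is 8% with SD 10. I read 8% as 8 points and assume that SD 10 applies to the change score; the SAP states it for the score. Allocation is 1:1. N is 13 in SAP 4.1 and 50 in the protocol. On the 0 to 100 KCCQ scale higher is better (Protocol 9.2.2), so benefit on both measures pushes r upward.

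**1. The plan's own figures.** S3 has no stated power, so I checked the two calculations whose inputs I reuse.
- Aim 1: difference in slopes over weeks 0, 4, 8 and 12, compound symmetry, 14 per arm. SD of the 12-week change implied by the slope = 12 × 19 × √(0.3/80) = 13.96. Then 15/(13.96 × √(2/14)) = 2.84, and Φ(2.84 − 1.96) = 81.1%. Stated: 81.1%.
- Aim 2: 8/(10 × √(2/25)) = 2.83, and Φ(2.83 − 1.96) = 80.7%; the noncentral t gives 79.1%. Stated: 80.2%.

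The inputs are understood.

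**2. What r can and cannot say.** For a Pearson r, slope = r × SD(KCCQ change)/SD(PA change), and the PA change matching 8 points is 8/slope. SD of PA change under the planning correlation = 19 × √(2 × (1 − 0.7)) = 14.7. With KCCQ SD 10 and PA-change SD assumed between 14.7 and 25:
- r = 0.3: 39 to 67 min/day
- r = 0.5: 24 to 40 min/day

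Without the SDs the reader has no figure in minutes. If Spearman is used, this conversion is not available at all.

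**3. What pooling adds.** Under 1:1 allocation the arm difference contributes covariance (15/2) × (8/2) = 30, and adds 7.5² = 56.25 to the PA variance and 4² = 16 to the KCCQ variance. With zero association within arms:
- PA-change SD 14.7: r = 30/√((216.6 + 56.25) × (100 + 16)) = 30/177.9 = 0.17
- PA-change SD 19: r = 30/√((361 + 56.25) × 116) = 30/220.0 = 0.14
- Half of each effect, SD 14.7: r = 7.5/√((216.6 + 14.06) × 104) = 7.5/154.9 = 0.05 (0.04 with SD 19)
- Either effect zero: r = 0

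A within-arm r of 0.10 becomes 0.22 to 0.25, and 0.30 becomes 0.40 to 0.42.

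**4. Precision at n = 13, for an observed pooled r of 0.5.** The 13 are treated as evenly split, which is an approximation.
- Correlation (Fisher z): 95% CI −0.07 to 0.82.
- Unadjusted slope with within-arm SDs: 0.5 × 10/14.7 = 0.340 per minute; SE = 0.340 × √(0.75/(0.25 × 11)) = 0.177; t(11) = 2.20. Per 15 min/day: 5.1 ± 5.9 points. With the arm-inflated SDs of 16.5 and 10.8 it is 4.9 ± 5.6.
- Arm-adjusted slope under the planned effects: within-arm covariance = 0.5 × 177.9 − 30 = 58.95; slope = 58.95/216.6 = 0.272; within-arm r = 0.40; SE = 0.272 × √(0.84/(0.16 × 10)) = 0.197; t(10) = 2.23. Per 15 min/day: 4.1 ± 6.6 points.

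**The case against.** The best defence is that the analysis does what the aim literally says. Aim 4 is to measure a correlation, S3 investigates a correlation, and the S3 hypothesis in Protocol 11.1.1 concerns only its direction. The study calls itself hypothesis generating, and its success rests on PA alone. The gap is with one sentence of rationale, and rewording that sentence would also close it. This stands, and it is why the fix offers that route.

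A reader might go further and infer that pooling is a mistake, or that any S3 correlation would be an artefact of treatment. The documents do not support that. The SAP chooses pooling openly. The pooled coefficient answers a legitimate question: whether patients whose PA rose more, for whatever reason, had larger KCCQ changes. If CR improves KCCQ through PA, the arm contrast is part of that association and an arm term would remove it. The induced r is also modest. Even 0.17 is below the smallest significant value (0.28 at N = 50, 0.55 at N = 13), and at half effects it falls below the SAP's lowest label.

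A reader might also want the strength labels removed. That is a preference, since a CI is planned beside the coefficient.

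It is fair to add that a slope at n = 13 is imprecise, and that it gives a number of minutes only for a stated size of KCCQ improvement, which S3 does not define. A slope in points per 15 min/day at least lets the reader apply any such size and shows the uncertainty in usable units. The patient-level listings in SAP section 7 would let someone derive a slope later, but that is not a planned result.

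**Conclusion.** The concern holds in this form. The planned S3 output cannot by itself supply the quantity that Protocol 9.1 says Aim 4 will determine, and this does not depend on any assumed value. The pooled coefficient also combines between-arm and within-arm information. With no association within arms, its expected value is 0.14 to 0.17 at the full planned effects, about 0.05 at half of each, and zero if either is absent. Those figures rest on reading 8% as 8 points, on a KCCQ-change SD of 10, and on a PA-change SD of 14.7 to 19. Pooling is a choice of estimand that should be reported beside an arm-adjusted estimate. This is a secondary aim, so the change is worth making but does not bear on trial success.

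**What to change.** In SAP 6.4, under S3, keep the pooled correlation and add a linear regression of KCCQ change on PA change. Report the slope as KCCQ points per 15 min/day with its 95% CI, once unadjusted and once with arm as a covariate, both labelled descriptive. State that the arm-adjusted slope may remove effect that acts through PA, which is why both are shown. Add the slopes to Tables 4.3.1 and 4.3.2.

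If no slope is to be reported, limit the purpose sentence for Aim 4 in Protocol 9.1 to estimating the strength of association.

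The cost is one extra regression and one degree of freedom for the arm term (10 rather than 11 residual degrees of freedom at n = 13). No new data are needed.
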